8.3.2 Outcome Assessment

Safety Outcomes

In BOAO Pilot Zone, the AEs recorded in the electronic health record database throughout the study period will be documented and analyzed. Detailed information in medical records including vital signs, concomitant treatments, results of routine laboratory testing, ECG, and radiology will be reviewed to verify these AEs. Severity grade of AEs will be further verified by investigators according to the Common Terminology Criteria for Adverse Events (CTCAE), version 5.0 (CTCAE v5.0).

The patient incidence of AE after sotorasib initiation, including:

- TEAE
- Adverse event of interest, inclusive of hepatotoxicity, interstitial lung disease/pneumonitis, and renal toxicity
- Treatment-related AEs
- Treatment-related AEs of grade 3 or worse
- Serious treatment-related AEs
- Treatment-related AEs leading to treatment discontinuation
- Treatment-related AEs leading to dose reduction
- Treatment-related AEs leading to death

[figure not shown]
In Hong Kong SAR CDARS database, only adverse event of interest, inclusive of hepatotoxicity, interstitial lung disease/pneumonitis, and renal toxicity will be documented and analyzed. Each event of interest is a grouping of individual preferred terms determined using the following standardized MedDRA queries (SMQs): drug-related hepatic disorders – comprehensive search (SMQ narrow) for hepatotoxicity; interstitial lung disease (SMQ narrow) for ILD/pneumonitis; and acute renal failure (SMQ narrow) for renal toxicity. Medical records including diagnosis, vital signs, concomitant treatments, results of routine laboratory testing, ECG, and radiology will be reviewed to identify and verify AE. Detailed testing and exams to review will be further clarified in the statistical analysis plan and eCRF.

Protocol Number: 20240175

Date: 27 March 2025 Page 23 of 47

OS

• OS: The time from the index date to death from any cause. Patients without evidence of death at data cutoff will be right-censored at their last activity date.

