In BOAO Pilot Zone, patients, often residing from across mainland China, need to be physically admitted to one of the several hospitals in BOAO Pilot Zone to receive sotorasib. The first hospitalization includes a complete medical history, radiology scans, tumor biomarker assessment, and liver and renal function tests to inform clinicians' decision to treat. As sotorasib is in the pre-registration program, the government requires close monitoring and reporting of safety events, which are well documented in the established hospital system. Hence, expectation that safety endpoints will be measured adequately in this study. As sotorasib is an oral medication taken daily until disease progression or unacceptable toxicity, patients need to physically return to the BOAO Pilot Zone hospital at least once per month initially, and every 3 months thereafter, to continue therapy. A case report form created for this study will be used to extract the relevant structured and unstructured data from the electronic heath record.

In Hong Kong SAR, the Clinical Data Analysis and Reporting System (CDARS) database will be used to identify patients treated with sotorasib at any public hospital. CDARS is a population-based database covering residents in Hong Kong SAR and can be linked to mortality records. Hence, the expectation that OS will be measured with complete follow-up. While the structure data within CDARS will provide most of the relevant data for study, the unstructured clinical notes within the electronic health record (Electronic Patient Record/Clinical Management System [EPR/CMS]) will also be used to augment information on key covariates.

Summary of Patient Eligibility Criteria

Inclusion Criteria:

- Adult (≥ 18 years) as of the index date.
- KRAS p.G12C-mutated locally advanced or metastatic NSCLC
- Received at least 1 dose of sotorasib.
- Receipt of at least 1 prior systemic therapy before use of sotorasib
- Obtained informed consent form (ICF), if required.

Exclusion Criteria:

Documentation of being a non-Chinese ethnicity.

Protocol Number: 20240175

Date: 27 March 2025 **Page 13 of 47**

Follow-up

Index date: sotorasib initiation date.

For objective of safety, CC

follow-up per patient

will continue through earliest date of:

- Last clinical activity in the data source
- Data cut-off in the data source:
 - BOAO Pilot Zone: Ethics Committee (EC) submission date
 (~ Q2 2025)
 - Hong Kong SAR: Data extraction cut-off date (~ Q3 2025)
- Death

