- Last treatment with sotorasib + 30 days

As the Hong Kong SAR CDARS database is a closed-loop database with linkage to the regional deaths registry, patients without evidence of death in the CDARS database by the data cut-off date were considered alive, and their last activity date will be the same as the cut-off date.

For objective of OS, follow-up per patient will continue through earliest date of last clinical activity in the data source, data cut-off in the data source, or death.

Variables

Outcomes:

- Primary: The patient incidence of AEs after sotorasib initiation.
- Secondary: OS from clinician notes in electronic health record and linkage to mortality records (where available).
- Exploratory: CCI

 CCI

Exposure:

o Use of sotorasib

Protocol Number: 20240175

Date: 27 March 2025 **Page 14 of 47**

Covariates

Key demographic, clinical characteristics, and pathology covariates including and not limited to age, sex, smoking status, body mass index (BMI), Eastern Cooperative Oncology Group (ECOG) performance status, histology, tumor stage, programmed death-ligand 1 (PD-L1) protein expression, presence of tumor mutations or rearrangements, laboratory test, electrocardiogram (ECG) and radiology, prior systemic treatments, brain metastases (if information available), prior lines of systemic therapy, and concomitant medications.

Study Sample Size

By the time of data cut-off, an estimated about 100 and 15 patients will have been treated with sotorasib and eligible for study inclusion from BOAO Pilot Zone and Hong Kong SAR, respectively. For a sample size of 115 patients and the observation of a proportion of 50% patients with an endpoint the largest level of margin of error (indicating the lowest level of precision) is \pm 9.14%.

Data Analysis

Frequencies will be presented for categorical demographic, clinical, and pathological variables. Descriptive statistics (mean, median, standard deviation, and range) will be presented for continuous variables.

The patient incidence of AEs will be summarized by count and proportions, specifically the proportion of patients experiencing AEs relative to the total number of patients. Median OS and PFS, along with the corresponding 95% confidence intervals (CIs) will be calculated using Kaplan-Meier estimates. The estimated survival probabilities, along with the corresponding 95% CIs will be presented for patients at 6 and 12 months.

CC

5. Amendments and Updates

None

6. Rationale and Background

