8.2.1 Study Period

The study eligibility period extends from the patients' index date (ie, the initiation of sotorasib) to the end of study period, defined as the earliest occurrence of patient's last activity date in the data source, data cut-off date or death.

The first available sotorasib use in BOAO Pilot Zone is around August 2021 through a pre-registration program. Specifically, sotorasib was included in the following hospitals'

Protocol Number: 20240175

Date: 27 March 2025 **Page 20 of 47**

drug lists and available for prescription: Ruijin Hainan Hospital in July 2022; BOAO Super Hospital in August 2021; BOAO Hengda Hospital in November 2021; and BOAO future Hospital in January 2022. The data cut-off will be the EC submission date (~ Q2 2025).

Sotorasib was approved in Hong Kong on April 29, 2022. The eligible treatment should occur after April 29, 2022. The data cut-off will be the date of data extraction (~ Q3 2025).

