8.7.2.2 Missing or Incomplete Data and Lost to Follow-up

This is a retrospective chart review study. Information which is not included in the patient medical charts cannot be reported. Missing data will not be replaced by imputation methods. All analyses will be conducted in patients with available information.

As described in Section 8.4, during the treatment period, physicians proactively follow up with patients in BOAO Pilot Zone. In addition, as advanced NSCLC is a life-threating disease which needs close support from physicians specialized in treating NSCLC, it is expected that patients remain at same site for treatment.

Outcome assessment up to the end of follow-up defined in Section 8.2.6 will be included in the analysis.

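### The protocol gives the BOAO safety endpoint two conflicting windows: the whole study period in Section 8.3.2, last treatment plus 30 days in the abstract

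*Protocol*

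**What the plan says.** **Window.** The BOAO paragraph of Section 8.3.2 (Safety Outcomes) states that "the AEs recorded in the electronic health record database throughout the study period will be documented and analyzed". Section 8.2.1 runs from the index date "to the end of study period, defined as the earliest occurrence of" the patient's "last activity date in the data source, data cut-off date or death". Stopping sotorasib is not among those end dates.

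The Follow-up part of the abstract (Section 4) gives safety its own rule, opening with "For objective of safety". Its list of earliest dates holds the same three ends and one more: "Last treatment with sotorasib + 30 days".

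Section 8.7.2.2 adds: "Outcome assessment up to the end of follow-up defined in Section 8.2.6 will be included in the analysis". The visible text of Section 8.2.6 holds the Hong Kong note on vital status and the overall survival rule.

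**Ascertainment.** For BOAO, Section 8.3.2 says that "results of routine laboratory testing, ECG, and radiology will be reviewed to verify these AEs". For Hong Kong, the same kinds of record "will be reviewed to identify and verify AE". Section 10.1.1 allows an abnormal laboratory finding to count as an adverse event.

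**The concern.** The primary objective is the patient incidence of adverse events, a simple proportion with no person-time denominator. Such a proportion depends directly on how long each patient is watched. Two programmers working from this protocol could count over different periods and both claim to follow it.

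The longer window would take in events after sotorasib has ended, including those under later therapy or advancing disease, and would raise the proportion without any change in the drug's safety. If the choice stays open until data are in hand, it may be made after results are seen. Section 8.7.1.1 plans an interim safety analysis after 30 BOAO patients.

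The difference in ascertainment matters for hepatotoxicity and renal toxicity, which often show first as laboratory changes. Events of interest are the only safety outcome documented in both regions.

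**Working it through.** **1. The passages side by side**

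| Place | Which adverse events | End of window |
|---|---|---|
| 8.3.2 with 8.2.1 | BOAO events, documented and analysed | last activity, cut-off or death |
| Abstract, Follow-up | safety objective | last activity, cut-off, death, or last treatment + 30 days |
| 8.7.2.2 | all outcome assessment | points to 8.2.6; only the survival rule is visible there |

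Reading 8.3.2 as wide capture with a narrower analysis does not work, because its sentence covers analysis as well as documentation. No visible text defines a treatment-emergent window that would settle the matter.

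**2. The plan's own precision figure**

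Section 8.5 uses e = 1.96 × √(p(1−p)/n). At p = 0.5 and n = 115, e = 1.96 × √(0.25/115) = 9.14%, as stated; the other four rows of Table 1 also reproduce. Section 8.7.2.1 analyses the regions separately, so the BOAO yardstick is n = 100: 1.96 × √(0.25/100) = 9.80%.

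**3. Illustration of the window effect**

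Inputs from the abstract's account of the phase III trial: median OS 10.6 months and median PFS 5.6 months. Assumptions, none of them from the protocol:
- PFS stands in for treatment time, since no treatment duration is given.
- Times are exponential.
- The event hazard r is constant and continues after treatment.
- Follow-up is capped at c = 12, 24 or 36 months.
- 30 days is taken as 1 month.

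Hazards: b = ln2/10.6 = 0.0654 per month for death; a = ln2/5.6 = 0.1238 for stopping or death; so a − b = 0.0584 for stopping while alive.

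Mean observed time:
- Study period: (1 − e^(−bc))/b
- Last treatment + 1 month: (1 − e^(−b))/b + e^(a−b) × (e^(−a) − e^(−ac))/a

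Patient incidence:
- Study period: r/(r+b) × (1 − e^(−(r+b)c))
- Last treatment + 1 month: r/(r+b) × (1 − e^(−(r+b))) + r·e^(a−b)/(r+a) × (e^(−(r+a)) − e^(−(r+a)c))

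| Cap (months) | Mean time, study period | Mean time, + 30 days | Share beyond | Incidence at r = 0.018 (short → long) | Incidence at r = 0.05 (short → long) |
|---|---|---|---|---|---|
| 12 | 8.32 | 6.60 | 21% | 10.95% → 13.65% | 26.57% → 32.48% |
| 24 | 12.11 | 8.10 | 33% | 12.96% → 18.67% | 29.89% → 40.61% |
| 36 | 13.84 | 8.44 | 39% | 13.33% → 20.51% | 30.30% → 42.65% |

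The shifts run from 2.7 points (13.65 − 10.95) to about 12.3 points (42.65 − 30.30). The largest exceed the 9.8-point BOAO margin of error.

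**4. Ascertainment**

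The BOAO sentence reviews results to verify *these* events, that is, events already recorded. The Hong Kong sentence also lets results identify events. Read literally, an uncharted laboratory abnormality in BOAO would not be added as a hepatic or renal event of interest. The documents give no figure for how often this happens, so no size can be derived.

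**The case against.** **The analysis rule may already be right.** Section 8.7.2.2 limits analysis to the follow-up in 8.2.6. In the abstract, the safety rule stands directly before the same two statements that remain in 8.2.6, so a matching safety rule may have been redacted there. This stands as a caution: a reader might infer that 8.2.6 lacks a safety rule, and the documents do not support that. It does not remove the conflict. If 8.2.6 repeats the abstract, Section 8.3.2 contradicts the body as well.

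**Most endpoints are bounded anyway.** Six of the eight listed endpoints need attribution to sotorasib. A reader might infer that the longer window inflates the whole safety profile; it bears mainly on treatment-emergent events and events of interest. This stands.

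**Off-treatment records may be sparse.** BOAO patients often live elsewhere and return to continue therapy, and 8.7.2.2 places proactive follow-up in the treatment period. The study period also ends at last activity in the data source, so the real difference may be smaller than the illustration. This stands.

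**The ascertainment wording has a reason.** BOAO has mandated safety reporting, whereas CDARS needs algorithms to find outcomes (8.6). A reader might infer that BOAO review can never add an event, but the protocol does not say so: Section 8.3.4 has adverse events abstracted manually from unstructured notes. Section 10.1.1 does not make every abnormal value an event, and with separate regional analyses and no hypothesis test, no planned contrast is corrupted. Section 8.3.2 also leaves the detail of tests to the SAP and eCRF, though that sentence is in the Hong Kong paragraph. Together these reduce the point to a secondary one.

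**Conclusion.** The window conflict holds on the text alone. Section 8.3.2 and the abstract give different ends to BOAO safety observation, and nothing visible reconciles them. The proportions at risk are those for treatment-emergent events and events of interest.

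The size is illustrative. Taking 21% to 39% of study-period time as lying beyond the shorter window, incidence would move by roughly 3 to 7 points at 0.018 events per month and 6 to 12 points at 0.05. No single figure should be taken as firm: the result depends on the follow-up cap, on PFS as a proxy for treatment time, on assumed hazards, and on a constant hazard after stopping, which is hard to defend for drug-related events.

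The ascertainment difference is real in the wording but supports only a supplementary analysis. A reader might infer a known under-count of hepatic and renal events in BOAO; the documents cannot show one.

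**What to change.** 1. In the BOAO paragraph of Section 8.3.2, replace the reference to the study period with *from index date to the end of safety follow-up*, as the abstract defines it: the earliest of last activity, data cut-off, death, or last treatment plus 30 days. Confirm that 8.2.6 carries the same rule.
2. Use that window for the BOAO incidence and list later recorded events separately.
3. In 8.3.2, use the identify-and-verify wording for both regions and apply the same SMQs to the events of interest. Report laboratory-derived hepatic and renal events as a supplementary analysis beside the as-recorded ones.

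Items 1 and 2 are nearly free. Section 8.3.1 already extracts treatment and discontinuation dates and says how to set the last treatment date when status is unclear. Item 3 needs post-index laboratory fields in the eCRF for about 100 patients and a short grading program. All of it should be settled before the interim analysis of 30 BOAO patients.

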Study feasibility within each available data source in China was evaluated in terms of available infrastructure to support execution of a real-world study, accessible data, ethical and security requirements, coverage and accuracy of critical covariates, completeness of follow-up for outcomes, and sample size of the target patient population. Based upon this evaluation, data sources in BOAO Pilot Zone and Hong Kong SAR were selected to be the most relevant to address the study objectives.

Protocol Number: 20240175

Date: 27 March 2025 **Page 11 of 47**

Objectives

Objectives	Endpoints		
Primary			
Characterize the safety profile of sotorasib.	The patient incidence of adverse events (AE) after sotorasib initiation, including:		
	 Treatment-emergent adverse events (TEAE) 		
	 Adverse event of interest, inclusive of hepatotoxicity, interstitial lung disease/pneumonitis, and renal toxicity 		
	o Treatment-related AEs		
	 Treatment-related AEs of grade 3 or worse 		
	o Serious treatment-related AEs		
	 Treatment-related AEs leading to treatment discontinuation 		
	 Treatment-related AEs leading to dose reduction 		
	 Treatment-related AEs leading to death 		
Secondary			
Describe real-world OS of sotorasib	OS from initial date of sotorasib use to date of death		
Exploratory			
CCI			

Hypothesis

Study objectives are descriptive in nature; no hypothesis will be tested.

Study Design

The study design is a retrospective cohort followed longitudinally for safety and effectiveness endpoints, based upon review of medical charts.

Protocol Number: 20240175

Date: 27 March 2025 Page 12 of 47

Study Population or Data Source

The target population is adult patients with *KRAS p.G12C*-mutated locally advanced or metastatic NSCLC and previously treated with at least 1 prior systemic therapy that have received sotorasib treatment in either location of BOAO Pilot Zone and Hong Kong SAR.

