The electronic health record database in BOAO Pilot Zone participating hospitals contain critical data relevant to the research question, for example the exposure of sotorasib, AEs, effectiveness outcomes, and key covariates. The electronic medical record (EMR) system in Hong Kong SAR contains both structured data, including demographic information, diagnosis, prescription records, procedure, hospital stay, discharge information, and unstructured data, including genetic testing results, radiographical and imaging exam results and additional patient information. Critical variables are covered and will be extracted to the extent possible.

Accuracy of the definition of exposure, outcomes, and covariates

Eligible patients need to be physically at BOAO Pilot Zone hospitals to receive treatments, enabling complete sotorasib exposure assessment in electronic health record databases. In addition, as advanced NSCLC is a life-threating disease which

Protocol Number: 20240175

Date: 27 March 2025 **Page 18 of 47**

needs close support from physicians specialized in treating NSCLC, it is expected that patients remain at same site in BOAO Pilot Zone for treatment. As sotorasib is used through the pre-registration program, local government authorities require close monitoring and reporting of safety events which were well documented in hospitals by physicians. Besides, physicians were reported to proactively follow-up with patients and document patients' treatment information, follow-up evaluations (both within and outside BOAO Pilot Zone), safety events, treatment outcome and discontinuation in hospital electronic health record database. These real-time data sources will be used to extract comprehensive and accurate outcome and key covariates.

Data will be verified using the data source by the study monitor and reviewed for consistency. All data extracted will be approved by the investigator at the investigational center. Adverse event grades and relationship to sotorasib may be unavailable or unconfirmable for some patients due to limitations in the available information. The level of missingness will be described and results related with grade will be interpreted with caution.

Sample size

The feasibility check indicates that at the data cut-off, approximately 100 sotorasib treated patients in BOAO Pilot Zone, and about 15 patients in Hong Kong SAR, will be eligible for inclusion. Details of sample size calculation are provided in Section 8.5.

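### In BOAO, all five AE endpoints on severity, seriousness, discontinuation, dose reduction and death count treatment-related events only, although relationship may be unknown, and no all-cause counterpart is listed

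*Protocol*

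**What the plan says.** The Abstract objectives table and Section 8.3.2 give the same eight safety endpoints, introduced by "The patient incidence of AE after sotorasib initiation, including". Two carry no causality condition: TEAEs, and AEs of interest (hepatotoxicity, ILD/pneumonitis, renal toxicity). One counts treatment-related AEs of any grade. The remaining five describe severity or consequence, and each is limited to related events:

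- for severity, "Treatment-related AEs of grade 3 or worse";
- for seriousness, the same restriction applies;
- for stopping of treatment, "Treatment-related AEs leading to treatment discontinuation";
- for a lowered dose, again only related events count;
- for fatal outcome, "Treatment-related AEs leading to death".

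These five apply to BOAO only, because for Hong Kong Section 8.3.2 confines safety to the AEs of interest.

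On data quality, Section 8.3.2 states that "Severity grade of AEs will be further verified by investigators according to the Common Terminology Criteria for Adverse Events". Section 6.3 concedes that "Adverse event grades and relationship to sotorasib may be unavailable or unconfirmable for some patients". Section 8.9.4 repeats this and says that both items will be extracted as far as possible and the level of missingness described. Section 8.7.2.2 rules out imputation and restricts analyses to patients with available information. Section 8.7.2.4 defines AE proportions over the total number of patients. Sections 8.7.3 and 10.2 tie the reported counts and proportions to the outcomes in Section 8.3.2.

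**The concern.** Section 10.1.1 defines an AE without regard to causality, and the primary objective is the whole safety profile. Yet each listed figure that tells a reader how bad the events were depends on relationship, an item the protocol expects to be incomplete. Attribution is also hard in this setting: there is no comparator, every patient has advanced cancer and prior systemic therapy, and Section 8.3.3 allows for sotorasib in combination.

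Two things are at stake. First, the missing-data rule and the denominator, read together, push the rates down: an event whose relationship is blank stays out of the numerator while its patient stays in the denominator. Second, with no all-cause figure beside the related one, a reader cannot tell a low rate of severe harm from incomplete attribution.

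**Working it through.** **1. The protocol's own precision figure.** Section 8.5 uses e = 1.96 × √(p(1 − p)/n). With p = 0.50 and n = 115, e = 1.96 × √(0.25/115) = 9.14%, as stated. The other four rows of Table 1 also reproduce (8.95, 8.38, 7.31 and 5.48%).

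**2. The margin that applies here.** The five endpoints are listed for BOAO only, and Section 8.7.2.1 analyses the regions separately, so n is about 100.

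- p = 0.50: 1.96 × √(0.25/100) = 9.80 points
- p = 0.33: 1.96 × √(0.2211/100) = 9.22 points
- p = 0.198: 1.96 × √(0.1588/100) = 7.81 points

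**3. Effect of unrecognised relationship.** Let p be the true proportion of patients with a related grade 3 or worse event. Let m be the fraction of those patients for whom no such event is recognised as related. If they count as not related over the full denominator, the reported rate is p(1 − m) and the bias is −pm. Section 6.2 supplies two reference rates: 33% grade 3 or worse in the phase III trial, and 19.8% treatment-related grade 3 in the phase II trial. The sentence giving the 33% does not itself label it treatment-related, so using it as p is an assumption. The protocol gives no value for m, so the range below is also an assumption.

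| m | p = 33%: reported (bias) | p = 19.8%: reported (bias) |
|---|---|---|
| 10% | 29.7% (−3.3) | 17.8% (−2.0) |
| 20% | 26.4% (−6.6) | 15.8% (−4.0) |
| 30% | 23.1% (−9.9) | 13.9% (−5.9) |
| 40% | 19.8% (−13.2) | 11.9% (−7.9) |

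The bias equals the sampling margin at m = 9.22/33 = 28% for the higher rate and m = 7.81/19.8 = 39% for the lower one.

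**4. Distance between related and all-cause.** The protocol gives no all-cause rate. If a share s of patients with a grade 3 or worse event have one judged related, the all-cause rate is p/s. For s = 80%, 60% and 50% (assumed), a related rate of 33% corresponds to 41%, 55% and 66%, and 19.8% corresponds to 25%, 33% and 40%. The listed endpoints cannot distinguish these cases.

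**5. Whether the data exist.** Section 8.3.2 has all recorded BOAO AEs documented, with grade verified for AEs in general. Section 8.3.1 extracts dates and reasons for dose reduction and discontinuation. The all-cause rows need no new fields and no more patients.

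**The case against.** The strongest reply is that this is analysis-plan detail. The list is opened by the word including, all BOAO AEs are collected and graded, and Section 8.7.2.1 leaves detailed analyses to a plan that is not shown. That plan may tabulate TEAEs by grade and seriousness, so absence from the list does not prove absence from the results. This stands as a caution. It does not remove the point, because Sections 8.7.3 and 10.2 commit the study only to the Section 8.3.2 outcomes, and the definition of primary endpoints belongs in the protocol.

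Other parts of the reply also stand:

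- The limitation is disclosed, and missingness will be described.
- Only under-recognition is modelled above. Over-attribution, plausible without a comparator, would push the other way.
- Up to 20% unrecognised, the bias lies within the sampling margin.
- All-cause rows are not free of judgement. Grade can be missing too, attributing a dose change to an event is itself a reading of the chart, and disease-related events are mixed in.
- Related-only figures match several of the trial results that the protocol cites.

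A reader might infer more than the text supports. It would be wrong to say that no result shows how many patients died, since overall survival counts death from any cause. That endpoint, however, does not isolate fatal AEs or deaths within 30 days of last treatment. Nor would an ILD event blamed on the cancer disappear: if recorded, it remains an AE of interest, and only its severity or fatal outcome goes without a listed endpoint. Nor do the documents show that abstractors assign relationship in retrospect. It is extracted from records, may have been assessed at the time of the event, and falls under the investigator approval of all extracted data in Sections 8.6 and 8.6.2.

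**Conclusion.** The point holds for the BOAO AE endpoints. All five on severity, seriousness, action taken and fatal outcome are related-only. Relationship is conceded to be incomplete, and the stated handling would probably count unknowns as not related. That last step is a reading of Sections 8.7.2.2 and 8.7.2.4 together: the available-information wording could instead drop such patients, and the protocol does not say which.

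The size is illustrative. With 10% to 40% unrecognised, the bias is −3.3 to −13.2 points on a 33% rate and −2.0 to −7.9 points on a 19.8% rate, against margins of ±9.2 and ±7.8 points. The recognition fractions, and the use of 33% as a related rate, are assumptions. What does not depend on them is that no listed endpoint gives the all-cause number of patients with grade 3 or worse, serious or fatal AEs on treatment. In a single-arm study with safety as its primary objective, this should be put right. The related-only endpoints themselves are legitimate, and which version is shown first is a matter of preference.

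**What to change.** In the Abstract endpoint table and Section 8.3.2, for BOAO, add an all-cause TEAE counterpart beside each of the five related-only endpoints: grade 3 or worse; serious; leading to discontinuation; leading to dose reduction; and leading to death up to the protocol's own safety limit of last sotorasib plus 30 days. State how events of unknown relationship enter the related-only numerators and denominators, and report their number. Report the number of discontinuations with unknown reason as a separate count, since an AE-based row cannot capture them.

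The cost is a few more table rows from fields already extracted. The all-cause rates will look less favourable and will include events due to the disease, which a footnote can say.
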